#### **Study Arms and Duration:**

Total duration of study participation for each participant is ~ 5 weeks (Screening 1-2 days; Treatment period is [REDACTED] days (2 doses daily Day 1 to Day 5) or 6 days (if only 1 dose received on Day 1) for a total of [REDACTED] doses; Follow-up period is [REDACTED]

CCI [REDACTED]. If the participant receives only one dose on day 1, dosing will continue until Day 6, to complete the [REDACTED] doses.

| Study Intervention(s)   |   |  |
|-------------------------|---|--|
| Intervention Name       | PF-07923568 (sisunatovir)   | Placebo for PF-07923568 (sisunatovir)  |
| Use                     | Experimental  | Placebo  |
| IMP or NIMP/AxMP        | IMP   | IMP  |
| Dose Formulation        | CCI [REDACTED] capsule dispersed in CCI [REDACTED] for oral ROA or nasogastric tube ROA | Matching Experimental dispersed in CCI [REDACTED] for oral ROA or nasogastric tube ROA |
| Unit Dose Strength(s)   | CCI [REDACTED] mg/mL (50 mg sisunatovir CCI [REDACTED] into CCI [REDACTED])             | Matching Experimental  |
| Route of Administration | Oral or nasogastric tube  | Oral or nasogastric tube   |
| Study Arm(s)            |   |  |
| Arm Title               | Sisunatovir   | Placebo  |
| Arm Description         | Participants will receive [REDACTED] doses of sisunatovir, CCI [REDACTED]               | Participants will receive [REDACTED] doses of placebo, CCI [REDACTED]                  |

#### Statistical Methods:

A sufficient number of participants will be screened to achieve approximately [REDACTED] evaluable participants randomized to study intervention across cohorts. The number randomized may be increased if Sponsor recommends repeating a dose, ie, an additional [REDACTED] active and [REDACTED] placebo may be enrolled in the same cohort. This totals to approximately a maximum of 108 evaluable participants ([REDACTED] in each cohort + [REDACTED] additional in each cohort if necessary) to be enrolled and receive study intervention. The sample size is empirically selected and is not based on statistical power calculation. The minimum number of participants (based on a minimum of [REDACTED] participants per Cohort) is approximately [REDACTED] evaluable participants as Cohorts 2 (2A, 2B, 2C, 2D) and 3 (3E, 3F, 3B, 3D) are optional in the study.

#### Safety Analysis:

All safety analyses will be performed on the safety analysis set, which is defined as all participants randomly assigned to study intervention and who take at least 1 dose of study

PFIZER CONFIDENTIAL

CT02-GSOP Clinical Protocol Template Phase 1 2 3 4 (14 April 2023)

Page 20

intervention. Participants will be analyzed according to the product (sisunatovir / placebo) they actually received.

AEs, blood pressure (BP), pulse rate, SpO2, and safety laboratory data will be reviewed and summarized on an ongoing basis during the study to evaluate the safety of participants. Any clinical laboratory or vital sign abnormality of potential clinical concern will be described. Safety data will be presented in tabular and/or graphical format and summarized descriptively, where appropriate.

#### **Pharmacokinetic Analysis:**

The final population PK model will be used to simulate plasma concentration-time curves for sisunatovir for individuals and to calculate post-hoc estimates of PK parameters (CL, Cmax, Cmin, AUC and t1/2) by age group.

The plasma concentrations of sisunatovir will be listed and descriptively summarized by nominal PK sampling time, treatment, age group, and cohort. Individual participant and summary profiles (mean and median plots) of the plasma concentrations data will be plotted by treatment, age group using actual and nominal times, respectively. Mean and median profiles will be presented on both linear and semi-log scales.

Data permitting, geometric means of PK parameters estimated from the final population PK model will be summarized descriptively by treatment and age group.

#### **Ethical Considerations:**

[figure not shown]
RSV is ubiquitous and is known to infect almost all children by 2 years of age. There is an unmet need for treatment of RSV infection and current management primarily consists of supportive care. The results of previous studies of sisunatovir support the investigation of sisunatovir for the treatment of RSV infection. The purpose of this double-blind, placebo-controlled study is to establish safety, tolerability, PK and guidance for dosing of sisunatovir in a pediatric population (up to 60 months) with RSV-LRTI for further clinical development of sisunatovir in the pediatric population.

The trial-specific risks and burdens for participants include the requirement for multiple visits, with one visit of extended duration, discomforts while undergoing study assessments (eg, blood draws, nasopharyngeal swabs), and the total blood volumes required. The study also includes the neonatal population with RSV-LRTI, with similar risks and burdens as described above. Based on clinical studies with sisunatovir thus far, gastrointestinal symptoms were the most commonly reported adverse events. Nonclinical studies suggested that the potential risks for sisunatovir may include cardiovascular, gastrointestinal, and hepatobiliary system effects. The doses proposed in this study provide exposures well below the PK stopping limit No Observed Adverse Effect Levels (NOAELs). Additionally, the proposed doses are targeting steady-state exposures comparable to CCI in adults, which were found to robustly decrease viral load and alleviate RSV symptoms relative to placebo (C5241002). Taking into account the measures to minimize risk to study participants, the potential benefit to participants with RSV-LRTI and the potential risks identified in association with sisunatovir, this dose-finding study is justified by the

anticipated benefits of sisunatovir in the clinical development of sisunatovir for the pediatric population with RSV-LRTI.

There are currently no approved RSV antivirals available, and thus no active control can be proposed as comparator. The comparator for this study is participants receiving placebo. Each cohort evaluated in the study will have participants on placebo. The placebo group is required for assessing the safety, tolerability, and palatability of the study intervention. All participants (including participants receiving placebo) enrolled in the study will receive the SOC.

## 1.2. Schema

- Cohorts in orange are optional.
- Total N can range from [REDACTED] to approximately a maximum 108 evaluable participants.
- N=[REDACTED] sisunatovir: [REDACTED] placebo) in Cohorts 1, 2 and 3 [REDACTED] (A, B, C and D in Cohorts 1 and Cohort 2; E, F, B and D in Cohort 3 [REDACTED]), minimum N of [REDACTED] sisunatovir: [REDACTED] placebo).
- Age band [REDACTED]

PFIZER CONFIDENTIAL

CT02-GSOP Clinical Protocol Template Phase 1 2 3 4 (14 April 2023)

Page 23

- Cohorts 1A, 1B, 1C can run concurrently.
- Cohort **CC1** randomized **CC1** reviewed by E-DMC.
- E-DMC data review for each Cohort after Day **CC1** completion.
- If Sponsor recommends repeating the dose, additional **CC1** active and **CC1** placebo may be enrolled in the same cohort (limit once per cohort).
- See Table 1 below for Cohort details.

### 1.2.1. Cohort Details

**Table 1. Cohort Details**

| Cohort          | Age Band | Timing of Cohorts    | Size*  | Dose   | Objective                          | Optional Cohort | E-DMC Concentration and Safety Review |
|-----------------|----------|----------------------|--|--|------------------------------------|-----------------|---------------------------------------|
| Cohort 1 |          |                      |  |  |                                    |                 |                                       |
| 1A              | CCI      | Parallel: 1A, 1B, 1C | CCI Active (total [REDACTED] doses) comparable to CCI [REDACTED] ) | CCI [REDACTED] (total [REDACTED] doses) comparable to CCI [REDACTED] ) | Assess safety, PK and tolerability | No              | Yes                                   |
| 1B              |          | Parallel: 1A, 1B, 1C | Active (Placebo);  | CCI [REDACTED] (total [REDACTED] doses) comparable to CCI [REDACTED] ) | Assess safety, PK and tolerability | No              | Yes                                   |
| 1C              |          | Parallel: 1A, 1B, 1C | Active (Placebo);  | CCI [REDACTED] (total [REDACTED] doses) comparable to CCI [REDACTED] ) | Assess safety, PK and tolerability | No              | Yes                                   |
| 1D              |          | After CCI            | Active (Placebo);  | CCI [REDACTED]   | Assess safety, PK and tolerability | No              | Yes                                   |

Table 1. Cohort Details

| Cohort          | Age Band       | Timing of Cohorts              | Size*                           | Dose  | Objective                               | Optional Cohort | E-DMC Concentration and Safety Review |
|-----------------|----------------|--------------------------------|---------------------------------|---|---|-----------------|---------------------------------------|
|                 |                |                                |                                 | CCI [REDACTED]  | and tolerability                        |                 |                                       |
| Cohort 2 |                |                                |                                 |   |   |                 |                                       |
| 2A              | CCI [REDACTED] | After CCI [REDACTED]           | CCI Active [REDACTED] Placebo); | Final determination of dose and dosing regimen by Sponsor | Dose-refinement or additional data      | Yes             | Yes                                   |
| 2B              | [REDACTED]     | After [REDACTED]               | Active [REDACTED] Placebo);     | Final determination of dose and dosing regimen by Sponsor | Dose-refinement or additional data      | Yes             | Yes                                   |
| 2C              | [REDACTED]     | After [REDACTED]               | Active [REDACTED] Placebo);     | Final determination of dose and dosing regimen by Sponsor | Dose-refinement or additional data      | Yes             | Yes                                   |
| 2D              | [REDACTED]     | After [REDACTED]               | Active [REDACTED] Placebo);     | Final determination of dose and dosing regimen by Sponsor | Assess safety, PK and tolerability      | Yes             | Yes                                   |
| Cohort 3 |                |                                |                                 |   |   |                 |                                       |
| 3E              | CCI [REDACTED] | After Cohort(s) CCI [REDACTED] | CCI Active [REDACTED] Placebo); | Based on Cohort(s) 1 and/or 2                             | Additional data in younger participants | Yes             | Yes                                   |
| 3F              | [REDACTED]     | After Cohort(s) CCI [REDACTED] | Active [REDACTED] Placebo);     | Based on Cohort(s) 1 and/or 2                             | Additional data in younger participants | Yes             | Yes                                   |

PFIZER CONFIDENTIAL

CT02-GSOP Clinical Protocol Template Phase 1 2 3 4 (14 April 2023)

Table 1. Cohort Details

| Cohort | Age Band | Timing of Cohorts   | Size*                    | Dose                          | Objective                               | Optional Cohort | E-DMC Concentration and Safety Review |
|--------|----------|---------------------|--------------------------|-------------------------------|---|-----------------|---------------------------------------|
| 3B     | CC1      | After Cohort(s) CC1 | CC1 Active CC1 Placebo); | Based on Cohort(s) 1 and/or 2 | Additional data in younger participants | Yes             | Yes                                   |
| 3D     |          | After Cohort(s) CC1 | Active CC1 Placebo);     | Based on Cohort(s) 1 and/or 2 | Additional data in younger participants | Yes             | Yes                                   |

\* In case of enrollment challenges: minimum CC1 Active CC1 Placebo); If Sponsor recommends repeating the dose: additional CC1 Active CC1 Placebo) permitted

### 1.3. Schedule of Activities

The SoA table provides an overview of the protocol visits and procedures. Refer to the **STUDY ASSESSMENTS AND PROCEDURES** section of the protocol for detailed information on each procedure and assessment required for compliance with the protocol.

The investigator may schedule visits (unplanned visits) in addition to those listed in the SoA table, in order to conduct evaluations or assessments required to protect the well-being of the participant.

#### 1.3.1. SoA

**Table 2. SoA**

| Visit Identifier   | Screen          | Treatment Period |                        |                        |                        | F/U                    |                        | ET                              | Notes  |
|--|-----------------|------------------|------------------------|------------------------|------------------------|------------------------|------------------------|---------------------------------|--|
| Abbreviations used in this table may be found in Appendix 12 (Section 10.12) | Day -1 to Day 1 | Day 1            | Day <small>CCI</small> | Prior to Day <small>CCI</small> | 

Day relative to start of study intervention (Day 1).

CCl visit to collect PK blood sample CCl post dose.

   |
| Visit Window   |                 |                  | +1 day                 | +1 day                 | ±2 days                | ±2 days                |                        | +1 day                          |  |
| Visit type   | CCl             |                  |                        |                        |                        |                        |                        |                                 | ET: if ET occurs after Day <small>CCI</small> visit, CCl visit allowed (follow Day <small>CCI</small> activities). ET prior to Day <small>CCI</small> should be in person visit (CCl). Day <small>CCI</small> visit can occur in person if needed. |
| Informed consent(s) for study, and assent (if appropriate)                                   | X               |                  |                        |                        |                        |                        |                        |                                 | 

Informed consent must be obtained prior to undergoing any study-specific procedures.

See Section 10.1.3.

   |
| Screen for inclusion/exclusion criteria  | X               | X                |                        |                        |                        |                        |                        |                                 | 

See Section 5.1 and Section 5.2.

For Argentina, see Exclusion Criterion 23.

  |
| Demographics   | X               |                  |                        |                        |                        |                        |                        |                                 | 

See Section 8.1.1.

   |
| Registration/ randomization  | X               | X                |                        |                        |                        |                        |                        |                                 | 

Randomization allowed on day of screening after completion of all screening assessments.

At registration, participant enrollment number and dose level allocation assigned.

                |
| Medical History and Physical Examination   |                 |                  |                        |                        |                        |                        |                        |                                 |  |

**Table 2. SoA**

| Visit Identifier   | Screen          | Treatment Period |                |                |                | F/U            |                | ET                      | Notes   |
|--|-----------------|------------------|----------------|----------------|----------------|----------------|----------------|-------------------------|---|
| Abbreviations used in this table may be found in Appendix 12 (Section 10.12) | Day -1 to Day 1 | Day 1            | Day CCI | Prior to Day CCI | 
 
Day relative to start of study intervention (Day 1).
 
CCI visit to collect PK blood sample CCI post dose.
 
   |
| Visit Window   |                 |                  | +1 day         | +1 day         | ±2 days        | ±2 days        |                | +1 day                  |   |
| Visit type   | CCI      |                  |                |                |                |                |                |                         | ET: if ET occurs after Day CCI visit, CCI visit allowed (follow Day CCI activities). ET prior to Day CCI should be in person visit ( CCI ). Day CCI visit can occur in person if needed.  |
| Medical history including background factors; Appendix 10B#1                 | X               |                  |                |                |                |                |                |                         | 
 
See Section 8.1.1 and Appendix 10B#1 in Section 10.10.2.
 
  |
| Collect social factors; Appendix 10B #2                                      | X               |                  |                |                | X              | X              | X              |                         | 
 
See Appendix 10B#2 in Section 10.10.2.
 
  |
| Physical Examination (recorded in source document)   | X               | X                |                | X              | X              | X              |                | X                       | 
 
Day 1 complete physical exam pre-dose.
 
After Day 1, brief physical exam.
 
See Section 8.3.1.
 
See Appendix 10C in Section 10.10.3 for suggested chronology of assessments.
 
                                 |
| Body Weight  | X               |                  |                |                | X              |                | X              |                         | 
 
See Section 8.3.1.
 
  |
| Length / Head Circumference  | X               |                  |                |                |                |                |                |                         | 
 
See Section 8.3.1.
 
  |
| Vital signs including SpO 2   | X               | X                |                | X              | X              | X              |                | X                       | 
 
Before PK, NP swabs and IMP administration (See Appendix 10C in Section 10.10.3 for proposed chronology of assessment).
 
If hospitalized collect once daily until discharge and per SoA after discharge. See Section 8.3.2.
 
 |
| 12-Lead ECG  | X               |                  |                |                |                |                |                |                         | 
 
ECG may be performed after screening as needed per investigator discretion.
 
See Section 8.3.3 for ECG details.
 
See Appendix 10C in Section 10.10.3 for proposed chronology of assessment.
 
                         |
| Record Supplemental O 2 need  | X               | X                | X              | X              | X              | X              | X              | X                       | 
 
See Section 8.3.2.3.
 
  |

PFIZER CONFIDENTIAL

CT02-GSOP Clinical Protocol Template Phase 1 2 3 4 (14 April 2023)

Page 28

**Table 2. SoA**

| Visit Identifier   | Screen          | Treatment Period |                   |                   |                   | F/U               |                   | ET                         | Notes   |
|--|-----------------|------------------|-------------------|-------------------|-------------------|-------------------|-------------------|----------------------------|---|
| Abbreviations used in this table may be found in Appendix 12 (Section 10.12) | Day -1 to Day 1 | Day 1            | Day cc | Prior to Day cc | 
 
Day relative to start of study intervention (Day 1).
 
CCl visit to collect PK blood sample CCl post dose.
 
   |
| Visit Window   |                 |                  | +1 day            | +1 day            | ±2 days           | ±2 days           |                   | +1 day                     |   |
| Visit type   | CCl             |                  |                   |                   |                   |                   |                   |                            | ET: if ET occurs after Day cc visit, CCl visit allowed (follow Day cc activities). ET prior to Day cc should be in person visit (CCl). Day cc visit can occur in person if needed.  |
| Lab Assessments  |                 |                  |                   |                   |                   |                   |                   |                            | 
 
See Section 8.3.4 for blood volumes and additional information.
 
See Appendix 2 in Section 10.2 for Clinical Laboratory tests to be done.
 
For laboratory collection volumes, see Section 8.3.4.
 
  |
| RSV Diagnostic Test  | X               |                  |                   |                   |                   |                   |                   |                            | Within cc hours of randomization See Sections 5.1, 8.1.  |
| Safety Labs (CBC, Chemistry)   | X               | X                | X                 | X                 |                   |                   | X                 |                            | 
 
CCl cohort CCl: liver function (AST, ALT, T bili) must be reviewed prior to Day cc dosing.
 
All other cohorts ( cc days old) should have the Day 1 pre-dose liver function tests (AST, ALT, T bili) ordered stat, if possible.
 
Safety labs can be done at screening or pre-dose on Day 1.
 
Pre-dose (Screening/Day 1) protocol-specified safety labs do not need to be repeated if performed as part of standard of care within 24 hours prior to first dose on Day 1. This includes labs conducted prior to signing of the ICD and these lab results will be entered in the CRF for the Screening/Day 1 visit.
 
Day cc and/or Day cc safety labs completed within the study specified window for that visit, do not need to be timed with the PK sample collection.
 
If Day cc safety labs are done on Day cc blood volume allowances should be reviewed prior to Day cc lab collections (see Table 7).
 
If ET occurs after Day cc visit, safety labs not required.
 
 |
| UA   | X               | X                |                   |                   |                   |                   |                   |                            | 
 
UA can be collected either at screening or Day 1, and at any time during the visit.
 
   |

PFIZER CONFIDENTIAL

CT02-GSOP Clinical Protocol Template Phase 1 2 3 4 (14 April 2023)

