| Added the statements below to exclusion criterion 11 in Section 1.1 and exclusion criterion 12 in Section 5.2:

First bullet point – “or expected to receive equivalent dose during study drug treatment.” Second bullet point – “or expected to receive treatment with these therapeutics during study drug treatment.” | To provide additional protocol clarification.   | Section 1.1 Synopsis and Section 5.2 Exclusion Criteria  |
| Removed pre-dose PK sample collection on Day  updated notes for PK blood sample in both Table 2 and Table 3, and updated Table 3 header.  | To reduce number of blood draws for PK samples required from 4 to 3, and to limit blood volume collected in the study.  | Section 1.3.1, Table 2 SoA, and Section 1.3.2, Table 3 Multiple Dose PK Days (For all Cohorts) |
| Non-Substantial Modifications  |   |  |
| Updated ClinicalTrials.gov ID to NCT06102174   | To provide the available information.   | Title page and Section 1.1 Synopsis  |
| Removed UA collection at Days  and   | C5241003 study collected urine samples and provided reassuring safety data. UA will still be collected at baseline and is one of the reflex tests (Table 8) to be done should there be concern for potential AKI.   | Section 1.3.1 SoA  |
| Removed CCI Services on Day    | To provide protocol clarification that CCI services will only be available at Day  visit and onwards.   | Section 1.3.1 SoA  |
| The frequency of collection of social factors was reduced to Screening, Day  Day  and ET visit, and Body Weight assessment was reduced to Screening, Day  and ET visit only.  | To simplify the number of assessments timepoints. The data entry for social factors is repetitive and cumulative data will be captured at the Day  and Day  visits. Repeated weight entries do not impact dosing, as dosing is determined based on baseline weight. | Section 1.3.1 SoA  |
| Removed Record RSV related Medical Visits on Days 2 and 3.   | To simplify study procedures  | Section 1.3.1 SoA  |

| Description of Change  | Brief Rationale   | Section # and Name              |
|--|---|---------------------------------|
| Reduced collection of SpO 2 to once daily for hospitalized participants.  | To be consistent with RSV signs/symptoms collection which is only once daily. |                                 |

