| Study Intervention and Other Treatments  |                                      |                  |  |  |   |  |  |   |  |
| Prior/concomitant treatment(s)   | X                                    | X                | →  | →  | →   | →  | X  | X   | 
 
See Section 6.9.
 
   |
| IMP administration   |                                      | X                | X  | X  | X   |  |  |   | 
 
CCI dosing Days 1 to CCI (Total CCI doses).
 
IMP (one dose) to be administered to participant during visit on Day 1, Day CCI and Day CCI.
 
For the day of extended post dose PK collection (Day CCI or Day CCI), the dose administered at visit must be in the morning for participants in an outpatient setting.
 
See Section 6.
 
See Appendix 10C in Section 10.10.3 for suggested chronology of assessments.
 
  |

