**Table 5. Differentiating DIKI and DICI in Pediatric Participants**

|               | AKI (including DIKI)
Any one of the below  | DICI  |
|---------------|---|---|
| Scys & Screat | Simultaneous, confirmed Scys increase of $\geq 0.3$ mg/L and confirmed Screat increase of $\geq 0.3$ mg/dL post-baseline.         | Confirmed Screat increase of $\geq 0.3$ mg/dL post-baseline without simultaneous confirmed increase of $\geq 0.3$ mg/L in Scys post-baseline. |
| Albuminuria   | Confirmed albuminuria increase (see Appendix 6 , Section 10.6 , for Grades A1 to A3 quantitation) | No albuminuria increase   |
| Urine volume  | Urine volume $<0.5$ mL/kg/h for 6 consecutive hours (if monitored)  | No urine volume decrease  |

Regardless of the presence or absence of increase in Screat, DIKI and other causes of AKI may be suspected if either there is (i) new-onset or worsening albuminuria or proteinuria are detected or (ii) urine volume (if measured) is  $<0.5$  mL/kg/h for 6 consecutive hours.

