3.1.3.1. Laboratory Data

The investigator must review the laboratory report, document this review, and record any clinically significant changes occurring during the study in the AE section of the CRF. Clinically significant abnormal laboratory test findings are those that are not associated with the underlying disease, unless judged by the investigator to be more severe than expected for the participant's condition.

To determine if there are any clinically significant laboratory abnormalities, the hematological and clinical biochemistry and other safety tests will be assessed against the criteria specified in the Pfizer reporting standards. This assessment will consider whether each participant's baseline test results are within or outside the laboratory reference range for particular laboratory parameter.

Baseline will be the last pre-dose measurement. Change from baseline (CFB) will be calculated for all post-baseline timepoints.

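### The only scheduled urinalysis may be taken after the first dose on Day 1, which leaves that child with no urine baseline under the SAP

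*Protocol*

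**What the plan says.** Protocol Table 2 (SoA) marks urinalysis at Screening and Day 1 only. Its note reads "UA can be collected either at screening or Day 1, and at any time during the visit", so one sample at either visit meets the requirement. The dosing row of the same table has "IMP (one dose) to be administered to participant during visit on Day 1".

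The row for blood count and chemistry carries a tighter note: "Safety labs can be done at screening or pre-dose on Day 1". That row is limited by its heading to those two panels, and urinalysis has its own row.

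SAP section 3.1.3.1 (Laboratory Data) says "Baseline will be the last pre-dose measurement. Change from baseline (CFB) will be calculated for all post-baseline timepoints". It also has the abnormality assessment take account of whether each participant's baseline result was inside or outside the reference range. SAP section 3.5 repeats the pre-treatment definition as the general rule and leaves room for stated exceptions. None is stated for urine.

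Protocol Table 8 lists urinalysis among the required tests, including urine albumin, urine creatinine and their ratio. Protocol Table 5, used when kidney injury is suspected, includes among its criteria "Confirmed albuminuria increase".

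**The concern.** The timing rule and the baseline definition do not fit together. The protocol permits the one planned urine to follow the first dose, and the SAP does not accept such a sample as a baseline. When that happens, two things are lost.

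- The single result is a post-dose value with no comparator. Protein, blood or ketones already present before any drug cannot be told apart from a change after dosing, and the SAP step that takes baseline status into account cannot be carried out.
- If a reflex urinalysis or albumin-to-creatinine ratio is triggered later, there is no pre-dose urine from which to judge whether albuminuria has risen.

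Laboratory abnormalities belong to the third primary endpoint, so it should be clear in advance which samples are baseline and which are not.

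**Working it through.** The plan gives no figure to reproduce: the study has no hypotheses, and its sample size is empirical. The check sets the provisions side by side.

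1. **Is a post-dose urine compliant?** Yes. The urinalysis note sets no order relative to dosing within the Day 1 visit, and the first dose falls in that visit.
2. **Does another provision impose a pre-dose condition?** None was found. The pre-dose limit in the SoA covers blood count and chemistry only. The suggested order of procedures in Appendix 10C ends with dosing but does not list urine collection.
3. **Is there a later scheduled urinalysis?** No. The current row has only Screening and Day 1. The Amendment 4 summary explains the removal of later collections by stating that "UA will still be collected at baseline and is one of the reflex tests (Table 8"). This is used here only as evidence of intent: the remaining sample was meant to be a baseline, but the note in force does not secure that.
4. **Can the SAP treat a post-dose sample as baseline?** Not under sections 3.1.3.1 and 3.5 as written. The visible reporting window in SAP Appendix 1.1 is the calendar day, so a post-dose Day 1 sample would carry the Day 1 label. Unless the collection time is recorded, it could be taken for a baseline by mistake.
5. **Can the value reach the primary endpoints?** It can, but need not. Protocol section 10.3.1 counts as an adverse event (AE) a condition first detected after dosing even if it may have been present earlier, and SAP section 3.1.1 flags events starting on or after the first dose as treatment-emergent. Against that, protocol sections 8.3.4 and 10.3.1 and SAP section 3.1.3.1 exclude findings associated with the underlying disease unless the investigator judges them more severe than expected.

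**Scale.** The number of children without a urine baseline is N × p. N is taken as the protocol maximum of 108, and p is the share whose only urinalysis follows the first dose. The documents do not give p, so the values below are assumptions.

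| Assumed p | 108 × p | Children |
|---|---|---|
| 10% | 10.8 | about 11 |
| 25% | 27.0 | 27 |
| 50% | 54.0 | 54 |

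If the sample must precede the first dose, the count falls to 0 apart from missed samples.

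**The case against.** The strongest reply is that little depends on this.

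- **Primary endpoint.** A reader might infer that urine findings due to the RSV illness will be counted as post-dose abnormalities or treatment-emergent events. The documents do not support that. Disease-related findings are excluded unless more severe than expected, so counting rests on the investigator's judgement. What stands is that this judgement is harder without a pre-dose value.
- **No planned comparison is lost.** With no later urinalysis scheduled, no child has a planned change from baseline in urine, and several dipstick items are qualitative only. This is correct. The loss concerns reflex or unscheduled tests and the reading of the single result.
- **Kidney criteria.** A reader might infer that the albuminuria criterion in Table 5 becomes unusable. That goes too far. Table 5 is a clinical aid and is not tied to the SAP baseline. Any one of its kidney-injury criteria is enough, and those based on serum markers and urine volume do not need urine albumin. Albuminuria also has absolute categories in section 10.6.3, the discontinuation criteria in Appendix 6 use serum creatinine, and a Day 1 urine remains available as an earlier value. What stands is narrower: that earlier value is not pre-dose.
- **Other sources of a baseline.** A screening urine closes the gap for that child, and section 8.1 may allow a qualifying routine-care sample to do so.
- **Unseen standards.** The sponsor's reporting standards may deal with a missing baseline. They are not in the documents, so this can be neither relied on nor ruled out.

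**Conclusion.** The mismatch is real in the current text. A child whose only urinalysis is a compliant post-dose Day 1 sample has no urine baseline under the SAP, and neither that value nor a later reflex urine test has a pre-dose comparator.

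Its weight is small. The share affected is not stated, and the range of about 11 to 54 children rests on an assumed 10% to 50% of the maximum 108. The documents do not say how often urine would be obtained late. A reader might also suspect bias between sisunatovir and placebo. Nothing supports this: the rule is the same in both randomised, blinded arms, so the expected effect is noise and misclassification in a descriptive safety summary. The point is worth fixing because the remedy is nearly free.

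**What to change.** **SoA, urinalysis note:** align it with the blood-test note, so that the sample is taken at screening or, where feasible, before the first dose on Day 1. Record the collection time relative to the first dose.

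**SAP section 3.1.3.1:** state that a first urinalysis taken after dosing is not a baseline, and that it will be listed or summarised separately with a flag for no baseline. It should not be relabelled as baseline, which would contradict the SAP's own definition. Nor should it be dropped, which would remove a post-exposure result from a primary safety summary.

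**Cost:** one sentence in each document, one recorded time and no extra sample. The downside is slightly less flexibility in when urine is collected. The SAP sentence is useful even for samples already collected, provided their times are known.
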